5.3.5.2 Persistent or Recurrent Adverse Events

A persistent adverse event is one that extends continuously, without resolution, between patient evaluation timepoints. The progression (increase and decrease) of an adverse event must be documented in the Adverse Event eCRF.

The initial severity of the event should be recorded, and the severity should be updated to reflect the most extreme severity any time the event worsens. If the event becomes serious, the Adverse Event eCRF should be updated to reflect this.

A recurrent adverse event is one that resolves between patient evaluation timepoints and subsequently recurs. Each recurrence of an adverse event should be recorded separately on the Adverse Event eCRF.

5.3.5.3 Abnormal Laboratory Values

Not every laboratory abnormality qualifies as an adverse event. A laboratory test result must be reported as an adverse event if it meets any of the following criteria:

- Accompanied by clinical symptoms
- Results in a change in study treatment (e.g., dosage modification, treatment interruption, or treatment discontinuation)
- Results in a medical intervention (e.g., potassium supplementation for hypokalemia) or a change in concomitant therapy
- Clinically significant in the investigator's judgment

It is the investigator's responsibility to review all laboratory findings. Medical and scientific judgment should be exercised in deciding whether an isolated laboratory abnormality should be classified as an adverse event.

If a clinically significant laboratory abnormality is a sign of a disease or syndrome (e.g., alkaline phosphatase and bilirubin 5 times the ULN associated with cholestasis), only the diagnosis (i.e., cholestasis) should be recorded on the Adverse Event eCRF.

If a clinically significant laboratory abnormality is not a sign of a disease or syndrome, the abnormality itself should be recorded on the Adverse Event eCRF, along with a descriptor indicating if the test result is above or below the normal range (e.g., "elevated potassium," as opposed to "abnormal potassium"). If the laboratory abnormality can be characterized by a precise clinical term per standard definitions, the clinical term should be recorded as the adverse event. For example, an elevated serum potassium level of 7.0 mEq/L should be recorded as "hyperkalemia."

Observations of the same clinically significant laboratory abnormality from visit to visit should not be repeatedly recorded on the Adverse Event eCRF, unless the etiology changes. The initial severity of the event should be recorded, and the severity or seriousness should be updated any time the event worsens or improves.

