5.3.5.4 Abnormal Vital Sign Values

Not every vital sign abnormality qualifies as an adverse event. A vital sign result must be reported as an adverse event if it meets any of the following criteria:

- Accompanied by clinical symptoms
- Results in a change in study treatment (e.g., dosage modification, treatment interruption, or treatment discontinuation)
- Results in a medical intervention or a change in concomitant therapy
- Clinically significant in the investigator's judgment

It is the investigator's responsibility to review all vital sign findings. Medical and scientific judgment should be exercised in deciding whether an isolated vital sign abnormality should be classified as an adverse event.

If a clinically significant vital sign abnormality is a sign of a disease or syndrome (e.g., high blood pressure), only the diagnosis (i.e., hypertension) should be recorded on the Adverse Event eCRF.

Observations of the same clinically significant vital sign abnormality from visit to visit should not be repeatedly recorded on the Adverse Event eCRF, unless the etiology changes. The initial severity of the event should be recorded, and the severity or seriousness should be updated any time the event worsens or improves.

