6.5 SAFETY ANALYSES

Safety analyses will include all patients who received at least one dose of study treatment, with patients allocated to the treatment arm associated with the regimen actually received.

Safety will be assessed through summaries of adverse events, changes in laboratory test results, changes in vital signs, and letrozole and GDC-0032 exposure.

Verbatim descriptions of adverse events will be mapped to thesaurus terms. Adverse event data will be listed by study site, treatment arm, patient number, and study day, severity, relationship to study drug, outcome, and action taken with the study treatments. Events occurring on or after treatment on Day 1 of Week 1 will be summarized by thesaurus term, appropriate thesaurus levels, and NCI CTCAE v4.0 grade. Serious adverse events, including deaths, will be listed separately and will be summarized.

Relevant laboratory and vital sign (heart rate, blood pressure, and temperature) data will be displayed by time, with NCI CTCAE v4.0 Grade 3 and 4 values identified, where appropriate. Additionally, all laboratory data will be summarized in tables by NCI CTCAE v4.0 grade.

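### Sections 5.3.5.3 and 5.3.5.4 let a laboratory or vital-sign adverse event be downgraded when it improves, in conflict with the worst-severity rule of Section 5.3.5.2

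*Protocol*

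**What the plan says.** Three neighbouring subsections of the protocol govern how the severity of an adverse event is kept up to date.

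Section 5.3.5.2 covers persistent events in general. Once the initial severity is entered, "the severity should be updated to reflect the most extreme severity any time the event worsens". Seriousness is treated in one direction only: "If the event becomes serious, the Adverse Event eCRF should be updated to reflect this". The same section also requires the course to be kept: "The progression (increase and decrease) of an adverse event must be documented in the Adverse Event eCRF".

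Section 5.3.5.3 covers laboratory abnormalities that qualify as adverse events: "The initial severity of the event should be recorded, and the severity or seriousness should be updated any time the event worsens or improves". It also limits the number of entries: one abnormality is entered once and not again at each visit, except where its cause is new. Section 5.3.5.4 gives vital signs the same limit on repeat entries and the same update rule: "the severity or seriousness should be updated any time the event worsens or improves". Neither section mentions the most extreme grade.

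For the analysis, Section 6.5 states that adverse events "will be summarized by thesaurus term, appropriate thesaurus levels, and NCI CTCAE v4.0 grade", with serious events summarized separately. It adds a second route for laboratory results: "Additionally, all laboratory data will be summarized in tables by NCI CTCAE v4.0 grade".

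**The concern.** The same kind of field on the adverse event form is governed by two rules that can leave different final values. Under the general rule the record ends at its peak. Under the laboratory and vital-sign rule it can end wherever the event last stood.

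Section 3.4.2 makes the incidence and severity of adverse events, serious adverse events and events of special interest the primary safety outcomes. If the record of a Grade 3–4 laboratory event is lowered once the value recovers, a table built on that record no longer counts it as Grade 3–4. If seriousness is lowered as well, the event leaves the serious-event summary. Whether an event met a seriousness criterion is a fact about its past, which later recovery does not change, yet the wording lets recovery be a reason to revise it.

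**Working it through.** The protocol gives no figure to reproduce here, so the check is a comparison of the rules and a trace of one event through them.

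**1. The rules side by side**

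| | Section 5.3.5.2 | Sections 5.3.5.3 and 5.3.5.4 |
|---|---|---|
| Severity is updated | on worsening | on worsening or improvement |
| Value it takes | the most extreme | not stated; on a plain reading, the current one |
| Seriousness is updated | when the event becomes serious | on worsening or improvement |
| Entries | one for a continuous event, a new one for each recurrence | one for the same abnormality, unless its cause changes |

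**2. Do both rules apply to the same event?** Yes. A laboratory abnormality that falls from Grade 3 to Grade 1 has not resolved. It is therefore a persistent event under Section 5.3.5.2 and also a laboratory event under Section 5.3.5.3. The protocol does not say which rule takes precedence.

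**3. Trace of one event.** Take a hyperglycemia event that reaches Grade 3 and then improves to Grade 1. Under Section 5.3.5.2 the severity stays at Grade 3 and the decrease is noted as part of the course. Under Section 5.3.5.3 the severity is updated again when the event improves, and because no second entry is made, that single record can end at Grade 1. The path is not unusual: Table 2 in Section 5.1.1.1 allows dosing to resume after Grade 3 or 4 hyperglycemia only after improvement to Grade 1 or below.

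**4. Which outputs are exposed?**
- The adverse event summary by grade in Section 6.5, for laboratory and vital-sign terms.
- The summary of serious events, where seriousness is revised after recovery.
- Two events of special interest in Section 5.2.3 that depend on a grade and on a laboratory value: Grade 4 hyperglycemia, and symptomatic hyperglycemia of Grade 3 or higher.

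**5. Which are not?** The other grade-defined events of special interest (colitis or enterocolitis, diarrhea, rash, pneumonitis) are clinical. They fall under Section 5.3.5.2, which keeps the peak.

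**6. Is the exposed group empty?** No. Section 1.7.1 lists 12 related Grade 3–4 terms for the letrozole combination cohort of 27 patients. Seven are laboratory terms: amylase, AST, alkaline phosphatase, gamma-glutamyltransferase, hyperglycemia, hypokalemia and lipase. Each is reported at 3.7%, which is one patient (1/27 = 3.7%). This shows that such events occur. It does not measure how many would be downgraded.

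**The case against.** The strongest defence is that updating need not mean overwriting. The disputed sentence asks for the initial severity and then for changes, and Section 5.3.5.2 requires decreases as well as increases to be documented. Both fit a form that stores a dated grade history, from which the peak could always be taken. The form is not shown, so a reader who infers that the worst grade is in fact erased goes further than the text. This part of the defence stands: the loss is possible, not established. But a documented course does not settle which grade the event carries into the tables, and Sections 5.3.5.3 and 5.3.5.4 do not say that the peak is kept.

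There are also other safeguards:
- Section 6.5 grades all laboratory data independently and identifies Grade 3 and 4 laboratory and vital-sign values over time.
- Serious events and events of special interest reach the safety department within 24 hours (Sections 5.2.2, 5.2.3 and 5.4).
- Table 9 in Section 5.3.3 makes every Grade 4 event reportable as serious.
- The data system keeps an audit trail (Section 7.1).

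These reduce the risk without removing it. Laboratory tables hold measured values, not the causality, seriousness or grade of the event. Expedited reporting does not stop a later change on the adverse event form. Nothing says that the summaries draw on the audit trail.

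A reader might also infer that the toxicity of GDC-0032 as a whole is understated and the difference between arms reduced. The documents do not support this. The rule applies to both arms, and the most frequent related events with letrozole, led by diarrhea at 67%, are clinical and outside it. Equal downgrading would narrow an absolute difference in laboratory events only if those events were commoner on GDC-0032 and were in fact downgraded.

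Finally, it is tempting to put a number on the effect. Half of 330 patients is 165, and the Grade 3–4 hyperglycemia rates of 3.7% and 14% in Section 1.7.1 would give 165 × 0.037 ≈ 6 to 165 × 0.14 ≈ 23 events. That range is not a valid size. The 14% comes from the fulvestrant cohort. The rates come from small daily-dosing cohorts at 6 and 9 mg, whereas this trial gives 6 mg on 5 days of 7 and excludes patients with raised fasting glucose or medicated diabetes. The product also assumes that every event improves and that every site lowers the grade.

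**Conclusion.** The point holds as an inconsistency that is wrong as written. Sections 5.3.5.3 and 5.3.5.4 conflict with Section 5.3.5.2 on which severity and seriousness the record should carry. A site that follows the former literally can leave a laboratory or vital-sign event below its peak grade or marked non-serious.

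The consequence is a possible understatement in the Section 6.5 adverse event summaries and in the two hyperglycemia events of special interest. It is limited to laboratory and vital-sign events. It depends on the form holding one current value, or on the summaries using the last value, and the protocol settles neither. Its size cannot be derived from the document.

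That the worst grade may be chosen in an analysis plan not shown here is no answer by itself, because an analysis can select only a grade that the record has kept. The absence of a tabulation convention from the protocol is not counted as a fault.

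**What to change.** In Sections 5.3.5.3 and 5.3.5.4, replace the update sentence by the rule of Section 5.3.5.2: enter the initial severity, move it to the most extreme severity when the event worsens, and do not lower severity, or seriousness once met, when the event improves. Record improvement as a dated grade change or as the outcome of the event. Base the adverse event summaries in Section 6.5 on that most extreme grade.

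The cost is a change of wording in two sections, a matching line in the form completion manual, and a statement in Section 6.5 or the analysis plan. No further data are collected.

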5.3.5.4 Abnormal Vital Sign Values

Not every vital sign abnormality qualifies as an adverse event. A vital sign result must be reported as an adverse event if it meets any of the following criteria:

- Accompanied by clinical symptoms
- Results in a change in study treatment (e.g., dosage modification, treatment interruption, or treatment discontinuation)
- Results in a medical intervention or a change in concomitant therapy
- Clinically significant in the investigator's judgment

It is the investigator's responsibility to review all vital sign findings. Medical and scientific judgment should be exercised in deciding whether an isolated vital sign abnormality should be classified as an adverse event.

If a clinically significant vital sign abnormality is a sign of a disease or syndrome (e.g., high blood pressure), only the diagnosis (i.e., hypertension) should be recorded on the Adverse Event eCRF.

Observations of the same clinically significant vital sign abnormality from visit to visit should not be repeatedly recorded on the Adverse Event eCRF, unless the etiology changes. The initial severity of the event should be recorded, and the severity or seriousness should be updated any time the event worsens or improves.

5.3.5.5 Abnormal Liver Function Tests

The finding of an elevated ALT or AST ($> 3 \times \text{ULN}$) in combination with either an elevated total bilirubin ($> 2 \times \text{ULN}$) or clinical jaundice in the absence of cholestasis or other causes of hyperbilirubinemia is considered to be an indicator of severe liver injury. Therefore, investigators must report as an adverse event the occurrence of either of the following:

- Treatment-emergent ALT or AST $> 3 \times \text{ULN}$ in combination with total bilirubin $> 2 \times \text{ULN}$
- Treatment-emergent ALT or AST $> 3 \times \text{ULN}$ in combination with clinical jaundice

The most appropriate diagnosis or (if a diagnosis cannot be established) the abnormal laboratory values should be recorded on the Adverse Event eCRF (see [Section 5.3.5.1](#)) and reported to ABCSG safety department immediately (i.e., no more than 24 hours after learning of the event), either as serious adverse event or a non-serious adverse event of special interest (see [Section 5.4.2](#)).

5.3.5.6 Deaths

All deaths that occur during the protocol-specified adverse event reporting period (see [Section 5.3.1](#)), regardless of relationship to study drug, must be recorded on the Adverse Event eCRF and immediately reported to ABCSG safety department (see [Section 5.4.2](#)). This includes death attributed to progression of breast cancer.

Death should be considered an outcome and not a distinct event. The event or condition that caused or contributed to the fatal outcome should be recorded as the single medical concept on the Adverse Event eCRF. Generally, only one such event should be reported. The term “sudden death” should only be used for the occurrence of an abrupt and unexpected death due to presumed cardiac causes in a patient with or without preexisting heart disease, within 1 hour of the onset of acute symptoms or, in the case of an unwitnessed death, within 24 hours after the patient was last seen alive and stable. If the cause of death is unknown and cannot be ascertained at the time of reporting, “unexplained death” should be recorded on the Adverse Event eCRF. If the cause of death later becomes available (e.g., after autopsy), “unexplained death” should be replaced by the established cause of death.

5.3.5.7 Preexisting Medical Conditions

A preexisting medical condition is one that is present at the screening visit for this study. Such conditions should be recorded on the General Medical History and Baseline Conditions CRF.

A preexisting medical condition should be recorded as an adverse event only if the frequency, severity, or character of the condition worsens during the study. When recording such events on the Adverse Event eCRF, it is important to convey the concept that the preexisting condition has changed by including applicable descriptors (e.g., “more frequent headaches”).

5.3.5.8 Hospitalization or Prolonged Hospitalization

Any adverse event that results in hospitalization (i.e., in-patient admission to a hospital) or prolonged hospitalization should be documented and reported as a serious adverse event (per the definition of serious adverse event in [Section 5.2.2](#)), except as outlined below.

The following hospitalization scenarios are not considered to be adverse events:

- Perform an efficacy measurement for the study
- Hospitalization for respite care
- Planned hospitalization required by the protocol for breast cancer surgery
- Hospitalization for a preexisting condition, provided that all of the following criteria are met:
 - The hospitalization was planned prior to the study or was scheduled during the study when elective surgery became necessary because of the expected normal progression of the disease
 - The patient has not suffered an adverse event
- Hospitalization due solely to progression of the underlying cancer
- Hospitalization for outpatient care outside of normal clinic operating hours that is required per protocol or per local standard of care
- Hospitalization for protocol mandated biopsies

5.3.5.9 Adverse Events Associated with an Overdose

An overdose is the accidental or intentional use of a drug in an amount higher than the dose being studied. An overdose or incorrect administration of study treatment is not itself an adverse event, but it may result in an adverse event. All adverse events associated with an overdose or incorrect administration of study drug should be recorded on the Adverse Event eCRF. If the associated adverse event fulfills serious criteria, the event should be reported to the ABCSG safety department immediately (i.e., no more than 24 hours after learning of the event; see [Section 5.4.2](#)).

5.3.5.10 Patient-Reported Outcome Data

Adverse event reports will not be derived from PRO data. However, if any patient responses suggestive of a possible adverse event are identified during site review of the PRO questionnaires, site staff will alert the investigator, who will determine if the criteria for an adverse event have been met and will document the outcome of this assessment in the patient's medical record per site practice. If the event meets the criteria for an adverse event, it will be reported on the Adverse Event eCRF.

5.4 IMMEDIATE REPORTING REQUIREMENTS FROM INVESTIGATOR TO ABCSG

Certain events require immediate reporting to allow ABCSG safety department to take appropriate measures to address potential new risks in a clinical trial. The investigator must report such events to ABCSG safety department immediately; under no circumstances should reporting take place more than 24 hours after the investigator learns of the event. The following is a list of events that the investigator must report to ABCSG safety department within 24 hours after learning of the event, regardless of relationship to study drug:

- Serious adverse events
- Non-serious adverse events of special interest
- Pregnancies

The investigator must report new significant follow-up information for these events to ABCSG safety department immediately (i.e., no more than 24 hours after becoming aware of the information). New significant information includes the following:

- New signs or symptoms or a change in the diagnosis
- Significant new diagnostic test results
- Change in causality based on new information
- Change in the event's outcome, including recovery
- Additional narrative information on the clinical course of the event

Investigators must also comply with local requirements for reporting serious adverse events to the local health authority and IRB/EC.

5.5 FOLLOW-UP OF PATIENTS AFTER ADVERSE EVENTS

5.5.1 Investigator Follow-Up

The investigator should follow each adverse event until the event has resolved to baseline grade or better, the event is assessed as stable by the investigator, the patient is lost to follow up, or the patient withdraws consent. Every effort should be made to follow all serious adverse events considered to be related to study drug or trial-related procedures until a final outcome can be reported.

During the study period, resolution of adverse events (with dates) should be documented on the Adverse Event eCRF and in the patient's medical record to facilitate source data verification (SDV). For follow-up reports of serious adverse events and non-serious adverse events of special interest, investigators should record all follow up information immediately (i.e., within 24 hours) on the paper Serious Adverse Event reporting form and transmit to ABCSG safety department via fax. In addition the serious adverse event and non-serious adverse event of special interest follow-up information will be captured in the EDC system. If, after follow-up, return to baseline status or stabilization cannot be established, an explanation should be recorded on the Adverse Event eCRF and paper Serious Adverse Event form, if applicable.

All pregnancies reported during the study should be followed until pregnancy outcome, and they should be reported according to the instructions provided in [Section 5.4](#).

5.5.2 Sponsor Follow-Up

For serious adverse events, non-serious adverse events of special interest, and pregnancies, the Sponsor and/or ABCSG safety department or a designee may follow up by telephone, fax, electronic mail, and/or a monitoring visit to obtain additional case details and outcome information (e.g., from hospital discharge summaries, consultant reports, autopsy reports) in order to perform an independent medical assessment of the reported case.

5.6 POST-STUDY ADVERSE EVENTS

At the time of study completion or study discontinuation, the investigator should instruct each patient to report to the investigator any subsequent adverse events that the patient's personal physician believes could be related to prior study drug treatment or study procedures.

The investigator should report these events directly to Genentech Safety Risk Management via telephone at [name].

5.7 EXPEDITED REPORTING TO HEALTH AUTHORITIES, INVESTIGATORS, INSTITUTIONAL REVIEW BOARDS, AND ETHICS COMMITTEES

The Sponsor will promptly evaluate all serious adverse events and non-serious adverse events of special interest against cumulative product experience to identify and expeditiously communicate possible new safety findings to investigators, IRBs, ECs, and applicable health authorities based on applicable legislation.

To determine reporting requirements for single adverse event cases, the Sponsor will assess the expectedness of these events using the following reference documents:

- GDC-0032 Investigator's Brochure
- Local prescribing information for letrozole SmPC

The Sponsor will compare the severity of each event and the cumulative event frequency reported for the study with the severity and frequency reported in the applicable reference document.

Reporting requirements will also be based on the investigator's assessment of causality and seriousness, with allowance for upgrading by the Sponsor as needed.

An IDMC will monitor the incidence of the above-listed anticipated events during the study. An aggregate report of any clinically relevant imbalances that do not favor the test product will be submitted to health authorities.

